5.1.5 Other Endpoint Analyses

5.1.5.1 Analyses of Incidence of Emergency Room Visits, Hospitalizations, and Mortality

Incidence proportions for patients with at least 1 ER visit, at least 1 hospitalization, and mortality during each 6-month Follow-up interval will be reported along with 95% CLs. The denominator for each incidence proportion will be the number of patients enrolled in the

study at the beginning of that particular 6-month interval who also provide a non-missing response to the questionnaire item for each type of event.

The time to the first occurrence of a CS-related ER visit, time to the first occurrence of a CS-related hospitalization, time to the first occurrence of a CS-related ER visit or hospitalization, and time to mortality will be analyzed using the nonparametric Turnbull estimation method ([Turnbull, 1976](#)) for interval-censored data available in SAS PROC ICLIFETEST for each 6-month interval during Follow-up. These tables will display the number of patients still at risk at the beginning of the interval along with the number of events and censored observations within each interval. Estimates of the survival probability (the proportion of patients without the event) will be provided for the upper boundary of each interval, and these probabilities will also be displayed as figures. Estimated quartiles for event-free time (with 95% CLs) will be reported.

If death dates are available for the analysis of mortality, this analysis will be performed using the Kaplan-Meier method instead of the Turnbull method. Estimated quartiles for survival time (with 95% CLs) will be reported, and estimated survival probabilities will be displayed as Kaplan-Meier curves.

Details for all ER visits and hospitalizations, including the reason for the visit or hospitalization, will be provided in data listings.

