5.1.1 Survey Conduct

An electronic consent and survey questionnaire approved by an Institutional Review Board (IRB) will be used by RTI to program the online survey for the purpose of standardizing responses among patients.

Each patient will complete up to 7 web-based surveys over the duration of the study. Each survey is anticipated to take no more than 20 minutes on average.

All assessments, except mortality, will be patient-reported; medical records will not routinely be requested or reviewed as part of this observational study unless required for safety reporting purposes. As patient recall over time may be limited, partial responses as in the case of dates of onset, and/or estimates of numerical information will be accepted.

Participation in the study is contingent on continued use of XERMELO. Each survey will establish ongoing treatment with XERMELO and continued consent to study participation prior to subsequent data collection.

The initial survey is intended to gather Baseline information, which may include:

- Sociodemographics (age, year of birth, sex, race, ethnicity, education, geographic region)
- Current medical history as it relates to CS, NET burden, NET location, and related conditions
 - Location of NET
 - Date of diagnosis; CS and NET
 - CS-related hospitalization(s)
 - CS-related ER visit(s)
 - NET-related surgery (eg, tumor debulking, lysis of adhesions)
- Satisfaction with CS, CS-related diarrhea and/or flushing control prior to starting XERMELO, where applicable
- Height and weight
- Concomitant medication as it relates to the following:
 - Long-acting SSA therapy

- Use of rescue medication - short-acting SSA
- Systemic tumor-directed therapy
- Liver-directed therapy (eg, chemoembolization)
- WPAI-SHP

The initial survey should be completed no later than 30 days, and subsequent surveys should be completed no later than 14 days, after the unique survey link has been provided to the patient via e-mail. Patients will be asked to complete a survey every 6 months for up to 3 years. The following patient-reported data may be collected as described in [Appendix A](#):

- Satisfaction with CS, CS-related diarrhea and/or flushing control after initiating XERMELO, where applicable
- PGIC
- Concomitant medication as it relates to the following:
 - Change in use of rescue medication - short-acting SSA
 - Change in long-acting SSA therapy
 - Systemic tumor-directed therapy
 - Liver-directed therapy (eg, chemoembolization)

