8.2.1.7 Incidence of Mortality

The incidence of mortality will be tracked indirectly based upon information received by RTI.

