9.1 Adverse Events

This is an observational, noninterventional study assessing patients initiating treatment of XERMELO via web-based surveys. Given the indirect contact with patients, adverse event (AE) collection will be limited by the questions included in the survey.

Explorative objectives of CS-related hospitalizations and CS-related ER visits will be reported as AEs. All information will be captured as part of the web-based survey and will be reported to Sponsor using a format agreed by the Sponsor and RTI. Information related to these events will be patient reported, unless the event is designated by the Sponsor as requiring additional follow-up as described in [Section 9.4](#).

The AEs will be forwarded by the study team to the Sponsor within 24 hours of the completion of a survey using the following e-mail address.

E-mail address (in case of fax failure): [REDACTED]

Patient mortality will be collected outside of this study as part of routine practice at the specialty pharmacies and will be received by the Sponsor on an ongoing basis as spontaneous reports and reported as such. These data will be reported in this study only as the study endpoint.

In case where an AE is received outside of the web-based surveys by the study team, an AE Report form will be completed and sent to the Sponsor at the above e-mail address within 24 hours of the study team's awareness of the AE.

Exposure (either maternal or paternal) to XERMELO during pregnancy, received either through or outside the web-based surveys, will be reported following the same process as that for the AEs, and additional information will be collected following the process described in [Section 9.5.1](#).

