11.5.3 Retention of Study Documents

The Investigator must not destroy any study-related records without receiving approval from the Sponsor. The Investigator must notify the Sponsor in the event of accidental loss or destruction of any study records. If the Investigator leaves the institution where the study was conducted, the Sponsor must be contacted to arrange alternative record storage options.

12. Administrative Structure of the Study

The study will be monitored by Sponsor personnel or Sponsor representative. The following functions for this study will be performed by organizations designated by the Sponsor: recruiting, data collection, data management, statistical analysis, and reporting.

13. Appendix A – Schedule of Events

	Baseline	Follow-up Period					
	Day 1	6 months	12 months	18 months	24 months	30 months	36 months
Tolerance (days)	+30	±14	±14	±14	±14	±14	±14
Informed consent	X						
Review and assess entry criteria (Section 6.1 and Section 6.2)	X						
Sociodemographics (Section 8.2.2.1)	X						
Height and weight (Section 8.2.2.2)	X						
Change in weight (Section 8.2.1.5)		X	X	X	X	X	X
Medical history: (Section 8.2.2.3)	X						
• Location of NET	X						
• Date of diagnosis; CS/NET	X						
• CS-related hospitalization and/or ER visit	X						
• NET-related surgery	X						
Satisfaction with CS control (Section 8.2.1.1) 0	X	X					
Satisfaction with CS-related diarrhea control (Section 8.2.1.1)	X	X					
Satisfaction with CS-related flushing control (Section 8.2.1.1)	X	X					
Patient Global Impression of Change (PGIC) Section 8.2.1.3		X					
Work Productivity and Activity Impairment – Specific Health Problem instrument (WPAI-SHP) Section 8.2.1.4	X	X					
Patient-reported CS-related hospitalization and emergency room visit (Section 8.2.1.6)	X	X	X	X	X	X	X
Review of Concomitant Medications: (Section 8.2.2.4)	X	X	X	X	X	X	X
• Rescue short-acting somatostatin analogs (SSAs)	X	X	X	X	X	X	X
• Long-acting SSAs	X	X	X	X	X	X	X
• Systemic tumor-directed therapy	X	X	X	X	X	X	X
• Liver-directed therapy	X	X	X	X	X	X	X

14. Appendix B – Ethical Standards

Ethics and Regulatory Considerations

This study will be conducted according to GCP, 21 CFR Part 50, (Protection of Human Subjects), 21 CFR Part 56 (Institutional Review Boards), International Conference on Harmonisation Guidance for Industry, E6 Good Clinical Practice: Consolidated Guidance, the Nuremberg Code, and the Declaration of Helsinki.

General Instructions

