3.2.5 Work Productivity and Activity Impairment Questionnaire—Specific Health Problem (WPAI-SHP)

The WPAI-SHP is a self-administered questionnaire ([Reilly et al., 1993](#)) comprising 6 questions that measure the effect of health problems on participants' ability to work and participate in regular activities based on their experiences in the previous 7 days. This questionnaire will be administered at Baseline and at the initial 6-month Follow-up.

The WPAI-SHP includes 4 domains (absenteeism, presenteeism, work productivity loss, and activity impairment). All participants will be asked whether they are employed (Q1) and how their CS-related problems affected their regular activities (Q6). Employed participants will be asked about hours of work missed due to CS-related problems (Q2), hours of work missed for any reason (eg, vacation, holidays, time off to participate in this study) (Q3), hours actually worked (Q4), and the degree that CS affected their productivity while working (Q5). An integer scale from 0 to 10 is used for Q5 and Q6, where 0 corresponds to no effect and 10 corresponds to complete effect.

Responses to the items are scored to produce the following 4 domains:

- Absenteeism: work time missed due to CS = [REDACTED]
- Presenteeism: impairment while working due to CS = [REDACTED]

- Work productivity loss: overall work impairment due to CS = [REDACTED]
[REDACTED]
- Activity impairment: activity impairment due to CS = [REDACTED]

Each score is then multiplied by 100 to express domains in terms of impairment percentages, with higher numbers indicating greater impairment and less productivity (ie, worse outcomes).

3.2.6 *Carcinoid Syndrome-related Health Care Resource Utilization*

At Baseline and at each Follow-up, questionnaire items will ask patients about ER visits and hospitalizations during the prior 6-month period. Data collected will include the following:

- The number of ER visits and the CS-related reason for each visit
- The number of hospitalizations, the number of nights for each stay, and the CS-related reason for each hospitalization

3.2.7 *Study Discontinuation and Mortality*

Patients will be terminated from the study if they discontinue the use of XERMELO, withdraw consent for participation, or are lost to follow-up. Information on reasons for discontinuation will be provided by the specialty pharmacy.

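### SAP 5.1.5.1 makes the interval mortality proportion depend on a questionnaire response, although no mortality item is described and deaths come from the pharmacies

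*SAP*

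**What the plan says.** SAP 5.1.5.1 lists three incidence proportions: at least one ER visit, "at least 1 hospitalization, and mortality during each 6-month Follow-up interval will be reported along with 95% CLs". One sentence then sets the denominator for all three. It begins: "The denominator for each incidence proportion will be the number of patients enrolled in the". Its remainder adds the timing and the response condition: "study at the beginning of that particular 6-month interval who also provide a non-missing response to the questionnaire item for each type of event". Mortality has no separate rule.

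The documents describe where each kind of event is recorded:

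- **ER visits and hospitalizations.** SAP 3.2.6 says that "questionnaire items will ask patients about ER visits and hospitalizations during the prior 6-month period". The schedule in Protocol Appendix A has a matching row, "Patient-reported CS-related hospitalization and emergency room visit", and no row for death.
- **Mortality.** Protocol 5.1.1 states: "All assessments, except mortality, will be patient-reported". Protocol 8.2.1.7 adds: "The incidence of mortality will be tracked indirectly based upon information received by RTI". Protocol 9.1 says: "Patient mortality will be collected outside of this study as part of routine practice at the specialty pharmacies". SAP 3.2.7 has the specialty pharmacy pass deaths on for analysis, either as counts per interval or by patient.

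Incidence of mortality at 6-month intervals is a named other endpoint (Protocol 10.3.2, SAP 2.3.3).

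**The concern.** The denominator rule fits events that a living patient reports at the end of the interval. It does not fit death, for which no item is described and which normally prevents return of the survey. Two analysts following the same sentence could therefore report different mortality proportions from the same data.

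At stake is the interval mortality figure, reported with 95% confidence limits. The mortality tables by satisfaction category in SAP 5.1.5.4 may also be affected if they reuse this denominator.

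**Working it through.** **1. Does another section supply the mortality denominator?**

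- Protocol 10.4.1 asks for mortality incidence per interval but names no denominator and sets no response condition.
- SAP 5.2 excludes missing data and makes no exception for deaths.
- SAP 5.1.2 requires data on at least one primary or secondary endpoint. All of these are assessed at month 6, so a literal reading would also remove patients who die before then.
- SAP 5.1.1 defers derivations to a separate specification, which may settle the point but is not part of the SAP.

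None of these repairs the rule.

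**2. What the sentence yields for mortality**

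- Literal: with no item, nobody meets the condition, and the denominator is empty or undefined.
- Survey returned: decedents drop out, except a patient who returns a survey early in the ±14-day window and then dies before the interval closes.
- The numerator is not stated. Decedents may leave both parts (toward 0%), or all reported deaths may be divided by respondents (too high).

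**3. The plan's own figures (SAP 2.4)**

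n = 1.96² × 0.5 × 0.5 / 0.05² = 384.16, rounded up to 385, as stated. Entry number: 385 / 0.60 = 641.7, or 642, against 643 stated; the difference does not matter here. These give 643 enrolled and 385 responding at month 6.

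**4. Size in the first interval**

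The documents give no death risk, so 2%, 5% and 10% are assumed. All deaths are captured, and all fall among the 258 non-respondents.

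| Assumed risk | Deaths | Deaths / 643 enrolled | Deaths / 385 respondents | Deaths / (385 + deaths) |
|---|---|---|---|---|
| 2% | 13 | 2.0% | 3.4% | 3.3% |
| 5% | 32 | 5.0% | 8.3% | 7.7% |
| 10% | 64 | 10.0% | 16.6% | 14.3% |

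The fourth column is 643/385 = 1.67 times the third. At 5% the excess is 3.3 points, against a sampling half-width of 1.96 × √(0.05 × 0.95 / 385) = 2.2 points.

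**5. How far this depends on the assumptions**

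- *1.67 is not a ceiling.* Let the 60% retained (385.8) include their own decedents: 0.05 × 385.8 = 19.3 deaths, leaving 366.5 respondents. With full capture, 0.05 × 643 = 32.15 deaths, and 32.15/366.5 = 8.8%, a ratio of 1.75.
- *Deaths known only among the retained:* 19.3/385.8 = 5.0%, or 19.3/366.5 = 5.3% if decedents do not respond. There is little or no inflation.
- *Assumed 10% non-response, full capture:* 32.15/578.7 = 5.6%, a ratio of 1.11. The 0.6-point excess is below the 1.8-point half-width at n = 579.

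**6. By satisfaction category (SAP 5.1.5.4)**

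Only patients with a month-6 satisfaction response enter, so only deaths after month 6 matter. With equal 5% risk and assumed response of 90% against 80%, full capture gives 0.05/0.90 = 5.6% and 0.05/0.80 = 6.3%, a ratio of 1.13. If deaths are known only among the retained, 0.045/0.855 and 0.040/0.760 are both 5.3%, a ratio of 1.00.

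**The case against.** The best defence is that a sensible analyst would apply the response condition only where an item exists. Mortality would then be divided by patients enrolled at interval start, and the separate specification could record this as a clarification. That may well be what was meant. But the sentence covers each proportion and each type of event, and nothing in the SAP exempts mortality. The defence also leaves open how to treat patients with unknown vital status.

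The second defence stands and lowers the weight of the point. The same section plans a Turnbull analysis of mortality (Kaplan-Meier if death dates are available). The Turnbull tables show numbers at risk, events and censored observations per interval, and neither method uses the disputed denominator. A mortality proportion near zero or far too high would visibly clash with them.

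A reader might infer more than the documents support:

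- *That mortality will be reported as 0%.* This needs patient-level deaths, so that decedents can be found and removed. SAP 3.2.7 allows aggregate counts, with which it cannot be done.
- *That 1.67 is the expected or the largest inflation.* It rests on full capture of deaths among patients who leave, and it changes with who counts as a respondent.
- *That the satisfaction comparison is compromised.* SAP 5.1.5.4 sets its own inclusion rule and does not cite this denominator. Reuse is possible but not stated, and the p-values are descriptive.

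**Conclusion.** The point holds as a minor one. As written, the mortality denominator in SAP 5.1.5.1 is either undefined or excludes nearly all patients who died in the interval. That much follows from the text and needs no assumed numbers.

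The size does rest on assumptions about death risk, response and completeness of death reporting. In the 5% illustration the error runs from negligible, when deaths are known only among retained patients, to about 3 points, when all deaths are captured and 385 of 643 respond. An interval without deaths is unaffected.

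The reach is one descriptive other endpoint, and possibly the later-interval mortality tables in SAP 5.1.5.4. The primary and secondary endpoints, the sample size and the Turnbull or Kaplan-Meier mortality analysis do not depend on this sentence.

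**What to change.** In SAP 5.1.5.1:

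1. Limit the questionnaire-response condition to ER visits and hospitalizations.
2. For mortality, divide deaths reported in the interval by all patients enrolled and alive at its start, regardless of survey return.
3. State that SAP 5.1.2 does not remove patients who die before month 6 from this analysis.
4. Report beside the proportion the number with unknown vital status at interval end. Say which records establish status, for example survey return, pharmacy report or the prescription fills that Protocol 5.1 collects for all enrolled patients.

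The cost is a few sentences and one extra table column.

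The downside is that the figure is too low if deaths among patients who leave are not captured. At a 5% risk with deaths known only among the retained, it reads 19.3/643 = 3.0%. If leavers had an assumed 10% risk, the true value would be 0.6 × 5% + 0.4 × 10% = 7.0%, and the figure would still read 3.0%. The unknown-status count, here 643 − 385.8 = about 257, shows how exposed it is.

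A denominator restricted to patients with ascertainable status should not be the main figure. Reported deaths always count as ascertained while surviving dropouts may not, which overstates risk: 7.7% against 5.0% in the last column of the table above.

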3.1 Background on Telotristat Ethyl (XERMELO®) and Carcinoid Syndrome (CS)

Well differentiated neuroendocrine tumor (NET), formerly known as carcinoid tumor, is a relatively rare tumor type that arises from cells of the neuroendocrine system (Kulke, 2011; Turaga, 2011; Yao 2008).

Carcinoid syndrome (CS) occurs when well differentiated NETs secrete large amounts of serotonin and other vasoactive products into the systemic circulation. By one estimate, CS develops in approximately 10% of adult patients with well differentiated NET and, with a few exceptions, only manifests itself in the presence of liver metastasis (Tomassetti, 2001). By another estimate, approximately 8% to 35% of patients with NET have associated CS, with tumors of the small intestine carrying the highest risk (Rorstad, 2005). Classically, symptoms associated with CS include flushing, diarrhea, wheezing, abdominal pain, and valvular heart disease, although, a variety of other symptoms can occur. Roughly 75% of patients with CS experience diarrhea, which can occur either with or without other manifestations of the syndrome, and has perhaps the most direct impact on activities of daily living (Moertel, 1987).

Valvular heart disease has been associated with high serotonin levels (as measured by its metabolite, urinary 5-hydroxyindoleacetic acid [u5-HIAA]). Due to the slow growing nature of NETs and the prolonged course of disease, about 50% of patients with CS will eventually develop heart disease. Usually only metastatic NETs result in pathological changes to the heart as a result of the hypersecretion of vasoactive substances; in these cases, the development of cardiac pathology heralds a more precipitous decline in clinical course (Fox, 2004; Gustafsson, 2008; Turaga, 2011).

In epidemiological studies, high levels of u5-HIAA in patients with NETs have been associated with poor survival. van der Horst Schrivers, et al prospectively studied 76 patients with midgut well differentiated NETs (van der Horst Schrivers, 2007). Urine collected over a 24 hour period every 3 months was tested for u5 HIAA levels. Patients with high u5-HIAA levels (>20 mmol/mol creatinine) had a median survival of 33 months compared with 90 months for patients with a moderately high level (≤ 20 mmol/mol creatinine) (hazard ratio=3.33; 95% confidence limit [CL]: 1.66-6.66; $p=0.001$) (Turaga, 2011).

Morbidity Associated with Carcinoid Syndrome

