10.4.1 Analyses of Study Endpoints

For the primary endpoint, the proportion of CS patients who are at least somewhat satisfied with their overall symptom control at 6 months, a point estimate and the corresponding 95% CLs will be calculated. Secondarily, a point estimate and corresponding 95% CLs will be calculated for the proportion of CS patients who are very satisfied with their overall symptom control at 6 months. The 95% CLs will be unadjusted and based on the assumption of approximate normal distribution. Missing data will not be imputed in the main analysis of the primary endpoint. As a sensitivity analysis, a patient with a missing response at 6 months will be imputed as a non-responder. This approach corresponds to non-responder imputation.

In addition to the point estimates and 95% CLs for the primary endpoint, the frequency distribution of the categorical responses, on a 5-point Likert scale, to patient satisfaction with overall symptom control at 6 months will be presented. The patient satisfaction measure will also be summarized as an ordinal variable with a value of 1 corresponding to “very dissatisfied” up to 5 corresponding to “very satisfied”.

All the secondary endpoints correspond to proportions and will be summarized through point estimates and 95% CLs, as described above for the primary endpoint. Frequency distributions of the categorical responses and summary statistics of the corresponding ordinal values of the categories will be presented. The handling of patients with a response of “not applicable” to patient satisfaction with CS-related diarrhea control or patient satisfaction with CS-related flushing control in the analysis will be described in the SAP.

The 4 WPAI-SHP scores at Baseline and month 6 will be summarized, as well as the change from Baseline to month 6.

The incidences of at least 1 CS-related hospitalization, at least 1 CS-related ER visit, and mortality after Baseline will be calculated at each 6-month interval. Kaplan-Meier estimates of each time-to-event variable, including quartiles, medians, and their corresponding 95% CLs, will be presented. The association or relationship between the primary endpoint and each long-term health outcome will be evaluated through descriptive statistics and the use of statistical models, as appropriate. Any statistical models that will be used and the appropriateness and/or limitations of their use will be described in the SAP.

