2 STUDY DESIGN AND OBJECTIVES

2.1 Study Design

This observational, noninterventional, single-arm study will include adult patients with CS who are initiating XERMELO as a new treatment. A minimum of 643 patients are expected to enroll.

A specialty pharmacy tasked with distributing XERMELO to patients will be responsible for the identification and recruitment of patients, and all eligible patients who are initiating treatment with XERMELO will be invited to participate in this study. Patients who enroll will be asked to complete up to 7 longitudinal, web-based surveys, including a Baseline assessment at enrollment, and a Follow-up survey every 6 months for up to 3 years. The Baseline questionnaire may be completed any time within a 30-day window following the electronic mail invitation to a patient to participate in the survey. The Follow-up surveys at 6-month intervals may be completed at any time within a \pm 14-day window.

Prescription fill data, type of insurance, and reasons for discontinuation, including mortality, will be collected directly from the specialty pharmacy using a process that is still being determined and will be described in a separate document.

A full description of the study design is found in the study protocol dated 19 May 2017 (Lexicon Pharmaceuticals, Inc.).

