5.1.5.4 Exploratory Analyses

Exploratory analysis of the association between patient satisfaction with overall CS symptom control at the initial 6-month Follow-up and the incidence of at least 1 ER visit, at least 1 hospitalization, and mortality will be performed as part of the final analysis. Only patients with non-missing data on satisfaction with overall CS symptom control at 6 months

will be included in the analysis. The satisfaction categories correspond to the binary categories used in the main analysis of the primary endpoint.

- Contingency table analysis to compare the incidence proportions of ER visits, hospitalizations, and mortality for each Follow-up interval and for the entire study period by satisfaction category, with chi-square tests for association. The satisfaction categories correspond to the binary categories used in the primary endpoint.
- Logistic regression models for the incidence of at least 1 ER visit and/or at least 1 hospitalization during the study period, with satisfaction category as a predictor variable. Covariates may be included in the models.

Additional or alternative exploratory analyses to be performed after data collection is complete will be determined in consultation with Lexicon and described in the final study report. The feasibility of each additional analysis will depend on the extent of data availability. Examples of additional analyses that may be considered are as follows:

- Kaplan-Meier analysis of mortality data, stratified by satisfaction category, including log-rank tests for differences between the strata.
- Kaplan-Meier analysis of time to first hospitalization, first ER visit, or mortality.
- Cox models for times to first ER visit, first hospitalization, and mortality, with satisfaction category as a predictor variable. Covariates may be included in the models.

Statistical tests will be 2-sided and have an associated alpha level of 0.05. The p-values from these tests will be considered descriptive rather than inferential.

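### SAP 5.1.5.1 gives no rule for death before a first CS-related ER visit or hospitalization; by default it is censored, and the curve's label then does not match what is estimated

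*SAP*

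**What the plan says.** SAP 5.1.5.1 lists time to first CS-related ER visit, time to first CS-related hospitalization, "time to the first occurrence of a CS-related ER visit or hospitalization, and time to mortality". These "will be analyzed using the nonparametric Turnbull estimation method" for interval-censored data. Death is therefore an endpoint of its own and is not part of the combined ER-or-hospitalization event.

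For each interval the tables show the number at risk and "the number of events and censored observations within each interval". There is no third status. The estimate at the end of each interval is introduced as "Estimates of the survival probability (the proportion of patients without the event", and quartiles with 95% CLs follow.

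Protocol 10.4.1 has the same gap: "Kaplan-Meier estimates of each time-to-event variable, including quartiles, medians, and their corresponding 95% CLs, will be presented". Neither document mentions competing risks or cumulative incidence.

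The one item that might bring death into the event is in SAP 5.1.5.4: "Kaplan-Meier analysis of time to first hospitalization, first ER visit, or mortality". It is an example of an analysis that might be considered later, and it does not say whether one composite or three separate endpoints are meant.

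SAP 3.2.7 allows deaths to arrive from the specialty pharmacy either as counts per 6-month interval or by patient, and dates may be absent.

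**The concern.** The label describes an observable quantity: the share of patients who have not yet had the event. A curve that censors deaths estimates something else, namely the probability of being event-free if death did not occur and if those who died would otherwise have had the same event risk as those who lived. A patient who dies without a hospitalization is one without the event, yet after censoring the estimator treats that patient as still exposed to later hospitalization.

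With "a Follow-up survey every 6 months for up to 3 years", in a disease where the protocol itself stresses mortality, the two quantities can separate by the later intervals. The long-term hospitalization and ER risks and the quartiles are the outputs affected. A reader who takes the label at face value would misread them as absolute risks.

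**Working it through.** **The plan's own figures.** None is stated for these analyses. The one design calculation, in SAP 2.4, concerns the primary endpoint: 1.96² × 0.25 / 0.05² = 384.1, so n = 385, and 385/0.6 = 641.7, or 642 against the stated 643. Nothing below affects it.

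**Direction, for recorded events.** Use the 6-month grid, with n at risk, e events and d deaths in each interval, and the same risk sets for both estimates.
- Deaths censored: S is the product of (1 − e/n), and one minus S grows in each interval by (previous S) × e/n.
- Death competing: the cumulative incidence grows by (previous F) × e/n, where F is the product of (1 − e/n − d/n).

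F can never exceed S, so one minus S is at least the cumulative incidence. It is strictly larger once an event is recorded in an interval after one with a death.

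**Inputs for size.**
- Mortality: Protocol 3.1 says that patients with high u5-HIAA "had a median survival of 33 months compared with 90 months for patients with a moderately high level". This is a 76-patient midgut NET study, not this cohort. With μ = ln 2/median, 36-month mortality is 53.1% (33 months) or 24.2% (90 months). A third case assumes 5% dead by month 36.
- Event risk: the documents give none. Assumed 12-month risk r = 10%, 20% or 40%, with λ = −ln(1 − r)/12.
- Constant, independent hazards.

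**Formulas.** Deaths censored: 1 − exp(−λt). Cumulative incidence: λ/(λ+μ) × [1 − exp(−(λ+μ)t)].

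Example with r = 20%, median 33 months, t = 36: λ = 0.01860 and μ = 0.02100. The censored version gives 1 − 0.8³ = 48.8%. The cumulative incidence is 0.4696 × (1 − exp(−1.4256)) = 0.4696 × 0.7596 = 35.7%.

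| Dead by month 36 | Assumed 12-month event risk | Deaths censored | Cumulative incidence | Excess (points) |
|---|---|---|---|---|
| 53.1% (median 33 months) | 10% | 27.1% | 19.4% | 7.7 |
| | 20% | 48.8% | 35.7% | 13.1 |
| | 40% | 78.4% | 60.2% | 18.2 |
| 24.2% (median 90 months) | 10% | 27.1% | 23.8% | 3.3 |
| | 20% | 48.8% | 43.3% | 5.5 |
| | 40% | 78.4% | 70.8% | 7.6 |
| 5% (assumed) | 10% | 27.1% | 26.5% | 0.6 |
| | 20% | 48.8% | 47.7% | 1.1 |
| | 40% | 78.4% | 76.9% | 1.5 |

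The largest excess in any of these nine cases is 1.3 points at month 6, 4.3 at month 12 and 11.6 at month 24.

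**Check on the survey grid.** A simulation of 1,000,000 patients at 20% annual risk, where the Turnbull estimate reduces to the product form above, gave 48.8% against a true 35.7% (33-month median) and 48.7% against 43.2% (90-month median).

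**Events lost before death.** Let q be the fraction of deaths without an earlier event that were immediately preceded by an event never reported. The true proportion with the event becomes (λ+qμ)/(λ+μ) × [1 − exp(−(λ+μ)t)], while the planned estimate stays the same. Setting the two equal at 36 months gives break-even values of q from 15% to 61% over the nine cases. In the simulation with the 33-month median and 20% annual risk, q = 25% gave a true 45.7% against an estimated 48.8%. With q = 50% it was 55.9% against 48.8%, so the sign had reversed.

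**The case against.** **Censoring is inferred.** A reader might infer that the SAP instructs that deaths be censored. It does not say so, and SAP 5.1.1 defers derivations to a separate specification that is not available here. This stands as a limit on the wording. It does not remove the gap: with two statuses and death outside the event definition, censoring is what a programmer following the text would do.

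**The direction is not settled.** A reader might infer that the long-term risks will be overstated. The documents do not support that without qualification. ER visits and hospitalizations are patient-reported for the prior 6 months (SAP 3.2.6), so a patient admitted who dies before the next survey never reports the admission. That pushes recorded risk down in the same patients, and a cumulative incidence built on the same reports would miss those events too. Stopping the drug also ends participation (Protocol 5.1.1; SAP 3.2.7), which is further censoring, possibly informative in either direction. Treating death as competing repairs neither problem.

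**The size is borrowed.** A reader might take the 13–18 points at 20–40% annual risk as the expected bias. Those figures pair an assumed event rate with the worse of two survival strata from another cohort. Because participation ends on stopping the drug or after a missed survey (Protocol 6.3), deaths while still participating may be fewer than population medians imply. Early on the excess is small: at 20% annual risk under the two medians it is 0.9–2.2 points at month 12, when the 95% half-width for a 20% proportion with 385 patients is about 4 points (1.96 × √(0.2 × 0.8/385)).

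**Partly covered already.** The plan also reports incidence proportions per interval, numbers at risk, and mortality separately. These help a reader but do not give a cumulative risk. The 5.1.5.4 example may be the event-or-death composite, but it is uncommitted and ambiguous.

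**Conclusion.** The point holds as a missing rule and a mismatched label. If the plan is followed as written, deaths before the first event are by default censored, and the curve is not then the share of patients free of the event. For recorded events, one minus the curve cannot fall below the cumulative incidence, and the gap widens with time. That part rests on algebra alone.

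The size is illustrative: about 8–18 points at month 36 with the 33-month median, 3–8 with the 90-month median, and 0.6–1.5 if only 5% die. It rests on constant independent hazards, assumed event risks and survival figures from a different NET population. The net error against the true risk could be smaller or of opposite sign, because of unreported events before death and censoring when the drug is stopped.

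These are descriptive other endpoints. The primary endpoint and sample size are unaffected. The change is worth making because the label invites an absolute-risk reading that the estimator does not support.

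**What to change.** In SAP 5.1.5.1:
- State how a death before the first ER visit or hospitalization is coded.
- Report cumulative incidence on the 6-month grid with death as a competing event (Aalen-Johansen form) for first hospitalization, first ER visit, and either.
- Make first CS-related hospitalization, ER visit or death a planned composite, and clear up the matching example in 5.1.5.4.

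This needs death status by patient and interval from the specialty pharmacy. SAP 2.1 and 3.1 say that the transfer process was still to be settled, so the requirement can be written into it.

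If only aggregate deaths are supplied, keep the Turnbull curve but remove the parenthetical label. State that deaths are censored and that events shortly before death may be missed. The second caveat belongs with the cumulative incidence as well.

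The cost is a few sentences of SAP text, one added procedure and a dependence on patient-level death data. The fallback is a wording change only.
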